## **2.5.3. Homework:**

### **2.5.3.1. PD-neurofeedback group:**

We will refine the scripts according to subjects' report on their most successful motor imagery strategies during neurofeedback runs in Visit 2, and ask them to practice these strategies at home for a total of 15 min every day (Tamir et al., 2007) between visits. Subjects will be provided a motor imagery diary and asked to keep a detailed log every day. We structured this diary based on the key elements of motor imagery practice including the duration, setting, content, and difficulty level of the

motor imagery exercise, as well as the type and quality of body sensations evoked by imagined movements (Collins and Carson, 2017).

#### **2.5.3.2. PD-control group:**

Subjects will continue practicing visual imagery-guided relaxation exercises at home and also be asked to keep a detailed log every day about the duration, setting, content, difficulty level, and the associated body sensations of these imagery exercises.

All subjects will receive daily reminders via text messages or emails to ensure adherence to daily imagery exercises.

### **2.6. Research Visit 3**

#### **2.6.1. Procedures for the PD-neurofeedback group:**

There will be no interference with the medication schedule. Subjects will take their dopaminergic medication as scheduled.

Subjects' diary entries and their overall experience with motor imagery will be reviewed and strategies for improvement and refinement will be discussed. Subsequently, subjects will complete 6-7 neurofeedback training runs as described in Visit 2. Subjects will again be instructed to continue practicing the successful motor imagery exercises at home as described in Visit 2.

#### **2.6.2. Procedures for the PD-control group:**

There will be no interference with the medication schedule. Subjects will take their dopaminergic medication as scheduled. Additional four surveys (Self-Efficacy, Self-regulation, Proactive Coping, Reflective Coping) and one cognitive rest battery specific for PD (SCOPA-COG) will be administered to match the study procedures (e.g., time spent with staff and engagement) between the PD-neurofeedback and PD-control groups. This additional material will be used as "filler" and will not interfere with any of the outcome measures or other study procedures.

Subjects' diary entries and their overall experience with visual imagery-guided relaxation will be reviewed and strategies for improvement and refinement will be discussed. Subjects will again be instructed to continue practicing the visual imagery exercises at home as described in Visit 2.

### **2.7. Research Visit 4:**

All subjects will be asked to temporarily hold the morning dose of their dopaminergic medications.

#### **2.7.1. Clinical Evaluation:**

The MDS-UPDRS part III motor examination and the standardized motor function tests will be repeated for all subjects. The MDS-UPDRS part III will be videotaped and the videos will be scored by a neurologist with movement disorders training ([name]), who is blind to subjects' group assignment.

Immediately after this final assessment, subjects will take their dopaminergic medication.

#### **2.7.2. Scanning:**

The resting-state fMRI scan for 10 min will be repeated for all subjects. Subjects will be instructed to keep their eyes closed and let their mind wander without focusing on a specific thought.

**2.7.2.1. PD-neurofeedback group:**

The control scan during which subjects perform motor imagery without neurofeedback will be repeated.

**2.7.2.2. PD-control group:**

The visual imagery scan, which is practically the same as the control scan, will be repeated.

**2.8. Resting-State Imaging Data Analysis****2.8.1. Resting-State Data Preprocessing:**

The Connectivity toolbox will be used for all resting-state data analysis steps (Whitfield-Gabrieli and Nieto-Castanon, 2012). Removal of the first four scans to reach magnetization steady state, motion correction, outlier detection, coregistration of functional scans with the anatomical scan, normalization to the standard MNI template, and smoothing with an 8-mm kernel to account for inter-individual anatomical variability will be performed. De-noising steps will include the elimination of signal originating from the white matter and cerebrospinal fluid, regression of motion artifacts and outliers from the time series, scrubbing, quadratic detrending, and bandpass-filtering ( $0.008 < f < 0.1$  Hz) to capture the fluctuations of the blood oxygenation level-dependent signal that typically occur within this frequency range at rest.

**2.8.2. Functional Connectivity Analysis:**

For each subject, the resting-state signal time courses will be extracted from the voxels within the right insula and dmFC masks, averaged, and correlated with those extracted from the regions of the whole brain atlas in the Connectivity toolbox using Pearson correlation. The correlation values will be Fisher z-transformed for second-level statistical analysis. This analysis will yield a correlation map for the right insula and dmFC separately for each subject.

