The PD-neurofeedback group will perform motor imagery of complex whole body movements (e.g., walking, jogging) in the scanner and focus on the kinesthetic aspects of motor imagery (i.e., body sensations evoked by the imagined movements). This task was chosen based on our preliminary data showing the involvement of the insula (sensation) and dmFC (movement) during kinesthetic motor imagery. Subjects will receive intermittent neurofeedback on their performance. The neurofeedback signal will be computed based on the functional connectivity strength between the subject's right insula and dmFC. The matched PD-control group will perform visual imagery (e.g., shapes, colors) in the scanner and will not receive neurofeedback. Subjects in both groups will also continue their respective imagery training at home. Hypothesis: The PD-neurofeedback group, but not the PD-control group, will

learn to increase the right insula-dmFC functional connectivity strength.

**Aim 2: To examine the effects of neurofeedback-guided motor imagery training on intrinsic functional connectivity of brain networks.**

We will obtain resting-state fMRI scans from the PD-neurofeedback and PD-control groups at baseline and post-training to examine the changes in intrinsic functional connectivity of the right insula and dmFC with the whole brain. *Hypothesis: Post-training, the intrinsic functional connectivity a) between the right insula and dmFC and b) of the right insula and dmFC with the whole brain, specifically with the motor cortical-striatal regions, will be significantly stronger in the PD-neurofeedback compared with the PD-control group.*

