### **2.5.1.2.3. Real-time Functional Connectivity Analysis:**

Previously, we used a silent heartbeat counting task during fMRI (Critchley et al., 2004) to functionally localize the insula and dmFC in a different group of subjects with mild PD (N = 10). Figure 3A shows the average group activations in the insula bilaterally (right>left) and dmFC. Our results are in line with previously reported activations in the insula and dmFC during the heartbeat counting task (Kurth et al., 2010; Simmons et al., 2013; Schulz 2016). We will create a cubic anatomical mask (6 x 6 x 6 mm) centered at the voxel with peak activity in the right insula (peak: x = 44, y = 4, z = 8) and dmFC (peak: x = -4, y = 2, z = 62). These anatomical masks will be created in the standard MNI brain space and then translated into each subject's functional space. Functional scans of each subject will be preprocessed and de-noised as described in Scheinost et al (2013b). The signal time course of the right insula and dmFC masks in a given subject will be computed as the average time course across all voxels within each of these masks. Finally, the time courses will be correlated and the r-values will be Fisher z-transformed. A Matlab program will plot the z-values as a bar and present them as neurofeedback (Figure 3B). The same procedures will be applied to the control scans with one exception: The z-values will be recorded, but not presented to the subjects as neurofeedback. Instead, subjects will see a horizontal white line.

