**Statistical Analyses:**

Demographic and clinical data: Independent-sample t-tests will be performed to compare the baseline values between the PD-neurofeedback and PD-control groups ( $p < 0.05$ , two-tailed).

**Aim 1:** A 2x2 mixed ANOVA with an interaction term will be performed to assess group differences in right insula-dmFC functional connectivity (between-subject factor: group, within-subject factor: right insula-dmFC functional connectivity during the first and last control scan, interaction: group x insula-dmFC functional connectivity). Post-hoc tests will be Bonferroni-corrected,  $p < 0.05$ .

**Aim 2:** Within-group one-sample t-tests will be performed on the right insula and dmFC resting-state functional connectivity maps. A 2x2 mixed ANOVA with an interaction term will be performed to assess group differences in resting-state functional connectivity (between-subject factor: group, within-subject factor: resting-state functional connectivity pre- and post-intervention, interaction: group x resting-state functional connectivity). All group analyses will be corrected for multiple comparisons using the false discovery rate procedure ( $p < 0.05$ , two-tailed) (Genovese et al., 2002).

**Aim 3:** The scores (i.e., time required for completion) of the motor function tests will be z-transformed and summed to obtain a composite motor function score for each subject. A 2x2 mixed ANOVA will be performed to compare the differences in motor functioning between the groups pre- and post-training (between-subject factor: group, within-subject factors: MDS-UPDRS motor exam and composite motor function scores, interaction: group x motor assessment). Post-hoc tests will be Bonferroni-corrected,  $p < 0.05$ .

**Exploratory Aims:** A paired-sample t-test will be performed to assess the differences in the whole-brain functional connectivity associated with the imagery and video-watching tasks. The results will be corrected for multiple comparisons using the false discovery rate procedure ( $p < 0.05$ , two-tailed) (Genovese et al., 2002).

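### Aim 2 hypothesis (a) predicts a change in one resting connection, but the plan specifies no direct test of it; the nearest planned test is an atlas-region proxy inside an FDR-corrected search

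*Combined protocol and SAP*

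**What the plan says.** The Statement of Purpose splits the Aim 2 hypothesis in two. Part (a) concerns "the intrinsic functional connectivity a) between the right insula and dmFC". Part (b) concerns each of the two regions with the whole brain, "specifically with the motor cortical-striatal regions".

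Section 2.8.2 sets out how resting connectivity is computed. Time courses are extracted from the two masks, averaged, and "correlated with those extracted from the regions of the whole brain atlas in the Connectivity toolbox using Pearson correlation". The stated output is two seed maps: "This analysis will yield a correlation map for the right insula and dmFC separately for each subject".

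Under Aim 2, Section 13 (Statistical Considerations) gives one-sample tests on the maps and one 2x2 mixed ANOVA, group by pre/post, on resting-state functional connectivity. It closes with "All group analyses will be corrected for multiple comparisons using the false discovery rate procedure" at 0.05, two-tailed.

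The plan does define a mask-to-mask value elsewhere. For the neurofeedback and control scans, section 2.5.1.2.3 builds the seeds ("We will create a cubic anatomical mask (6 x 6 x 6 mm) centered at the voxel with peak activity in the right insula", with a matching one for the dmFC) and correlates one with the other: "Finally, the time courses will be correlated and the r-values will be Fisher z-transformed". Aim 1 tests that single value, with "within-subject factor: right insula-dmFC functional connectivity during the first and last control scan".

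**The concern.** Hypothesis (a) asks whether the connection trained in the scanner is also stronger at rest. That is one number per subject per scan. The resting analysis as written does not produce that number, although the same plan produces it for the task scans and tests it in Aim 1.

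Three things follow. First, the closest quantity available is one mask against whichever atlas region contains the other site. That region is not the 6 x 6 x 6 mm trained cube. The plan does not say which region stands in, or whether the insula or the dmFC is the seed. Second, that proxy is one of many tests under FDR, so it faces a stricter threshold than a single planned comparison would. Third, with the variable undefined, the choice between mask-to-mask, insula-to-atlas and dmFC-to-atlas, corrected or not, can be made after the data are seen.

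At stake is the conclusion on carry-over to rest. A null whole-brain result could be reported as no transfer when the trained connection was never directly tested.

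**Working it through.** **Step 1: the two definitions side by side.**

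| | Task and control scans (2.5.1.2.3; Aim 1) | Resting scans (2.8.2; Aim 2) |
|---|---|---|
| Correlation | insula mask with dmFC mask | each mask with atlas regions |
| Output per subject | one Fisher-z value | two seed maps |
| Group test | 2x2 ANOVA on that value | 2x2 ANOVA on resting connectivity, variable not named |
| Correction | Bonferroni for post-hoc tests | FDR for all group analyses |

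Nothing in section 2.8 repeats or refers to the mask-to-mask step, and Section 13 names no exemption from FDR for (a).

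**Step 2: the plan's own figures.** No effect size, power or number of tests is given for Aim 2. The only sample-size figure, 22 subjects, is for the MDS-UPDRS motor score (5 points, SD 9, alpha 0.05, power 0.80). It reproduces as a one-sided, single-group t-test (n = 22, power 0.809). Below, 22 and the planned 30 per arm serve only as sample sizes. A further value, 19 per arm, is 30 less 35% drop-out: 30 x 0.65 = 19.5, rounded down.

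**Step 3: method.** In a 2x2 design the group x time interaction equals a two-sample t-test on change scores. With n per arm and standardised difference in change d, df = 2n - 2, the noncentrality is d x sqrt(n/2), and power is P(|T| > t(1 - alpha/2, df)). If the target is the only true effect among m tests, the FDR threshold for it is close to 0.05/m. The value of m is not in the documents; 50 to 400 is an assumption.

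Worked case, n = 22, d = 0.865: noncentrality = 0.865 x sqrt(11) = 2.87 and df = 42. The critical value is 2.018 at 0.05, giving power 0.80. At 0.05/100 it is 3.773, giving power 0.21.

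**Step 4: target is the only true effect, d set to give 80% power as a single test.**

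| n per arm | d | single test | m = 50 | m = 100 | m = 200 | m = 400 |
|---|---|---|---|---|---|---|
| 19 | 0.934 | 0.80 | 0.27 | 0.20 | 0.15 | 0.11 |
| 22 | 0.865 | 0.80 | 0.27 | 0.21 | 0.15 | 0.11 |
| 30 | 0.736 | 0.80 | 0.28 | 0.22 | 0.17 | 0.12 |

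**Step 5: the same d = 0.865 at the planned 30 per arm.** Power is 0.91 as a single test, and 0.46, 0.38 and 0.31 for m = 50, 100 and 200.

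**Step 6: other connections also change.** FDR relaxes its threshold as more true effects are present. A Benjamini-Hochberg simulation (6,000 runs per setting, 22 and 30 per arm, m = 50 to 400, correlation between tests 0 or 0.3) gives, against 80% for the single test:

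| Share of tests with the same effect | Power for the target |
|---|---|
| 10% | 34-41% |
| 25% | 48-53% |
| 50% | 61-66% |

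Steps 4 to 6 give the atlas proxy the same standardised effect as the mask-to-mask value. They therefore isolate the cost of the search and say nothing about any further gain or loss from using a different target region.

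**The case against.** The strongest reply is that the Aim 2 ANOVA sentence does not mention maps, unlike the one-sample tests before it, and runs parallel to Aim 1's single-value ANOVA. Both mask time courses are extracted anyway, and the mask-to-mask recipe exists in section 2.5.1.2.3. If the ANOVA were run on one insula-dmFC value, FDR over one test would leave its p-value unchanged. This stands in part. A reader might infer that (a) is ruled out or cannot be tested; the documents do not support that. They leave it unspecified. But the benign reading needs a resting variable that section 2.8.2 does not define.

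A reader might also take (a) to be the trial's only a-priori prediction. It is not. Hypothesis (b) names motor cortical-striatal regions in advance, and Aims 1 and 3 carry directional hypotheses.

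Nor do the documents support a single severe power figure. The effect size is illustrative, m and the FDR family (one seed or both) are not stated, and hypothesis (b) itself predicts changes elsewhere, which would soften the loss.

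The contrast between the trained cube and an atlas region is also less sharp than it looks: the atlas is not described, and resting data are smoothed with an 8-mm kernel, wider than the 6-mm mask.

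Finally, the consequence is bounded. Sample size and interim stopping rest on the motor outcome, and Aim 1 already tests the trained pair mask-to-mask during imagery.

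**Conclusion.** The point holds as a gap between hypothesis and analysis. Followed as written, the plan gives hypothesis (a) no direct test, only a proxy whose region and seed direction are not fixed in advance, judged within an FDR-corrected search.

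The direction of the power loss was the same in every scenario examined; its size is not known. Relative to 80% for a single test, it runs from severe (about 11-28% when the trained connection alone changes, over 50 to 400 tests) to moderate (about 61-66% when half the connections change equally). These ranges rest on an assumed effect size, an assumed number of tests and an equal effect for proxy and mask pair. The change should be made, because Aim 2 states (a) as a hypothesis of its own, but the point bears on a resting-state conclusion and not on the motor result that drives the trial.

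**What to change.** In section 2.8.2, add for each subject the Fisher-z correlation between the right-insula-mask and dmFC-mask resting time courses at Visits 2 and 4.

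In Section 13, Aim 2, test the group x time interaction on that value as one pre-specified comparison at two-sided 0.05 for hypothesis (a). Keep whole-brain FDR for hypothesis (b), and state the atlas, the number of regions and whether the two seeds form one FDR family or two. No covariates need be added for this purpose: baseline is already one of the two repeated values.

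The cost is a few lines of text and one extra correlation per resting scan from time courses already extracted; no new data are needed. The small downside is one additional Aim 2 test outside the FDR family, which the plan should state openly.

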**3. Research Strategy for the Exploratory Aims:**

**Subjects:** We plan on recruiting 15 new subjects with PD. Subjects who are interested in participating in the study will undergo medical history and MRI screening for eligibility in-person or via phone/email. The standard MRI Safety Questionnaire that was developed at the MRRC will be used. All experimental procedures will be completed in one research visit. Subjects will continue to take their PD medications as scheduled throughout the research visit.

**Clinical Evaluation:** [name] will perform an initial physical and neurological examination on all subjects. The diagnosis of idiopathic PD will be made according to the UK Brain Bank diagnostic criteria (Hughes et al., 1992). The Movement Disorders Society-Unified Parkinson's Disease Rating Scale (MDS-UPDRS) (Goetz et al., 2008) and Hoehn & Yahr staging (Hoehn and Yahr, 1998) will be used to determine disease severity and stage of PD subjects. The Montreal Cognitive Assessment test will be administered to rule out dementia (Nasreddine et al., 2005). Self-evaluation questionnaires will be administered including: Beck Depression Inventory-II (Beck 1997), Starkstein Apathy Scale (Starkstein et al., 1992), Spielberger State-Trait Anxiety Inventory (Spielberger et al., 1982), Parkinson disease Fatigue Scale (Brown et al., 2005), Parkinson disease quality of life scale (PDQ39) (Peto et al., 1995), and Self-Efficacy (Chen et al., 2011) and Self-Regulation (Schwarzer et al., 1999) scales. Imagery skills will be tested using the Questionnaire on Mental Imagery (Sheehan 1967).

**Hybrid Mental Imagery Practice:** Subjects will practice guided mental imagery of everyday task performance outside the scanner.

**Video-Watching Practice:** Subjects will watch sample video footage of everyday task performance outside the scanner for practice.

**MRI Parameters:** We will conduct the MRI experiments in a Siemens 3.0 Tesla human research

magnet in the MRRC. A 32-channel head coil will be used to collect high-resolution anatomical and echo planar images for fMRI. First, T1-weighted MPRAGE anatomical images (voxel size: 1 x 1 x 1 mm) will be collected for an accurate localization of the fMRI data. Then, axial, T2-weighted, echo planar functional images will be collected (voxel size: 3.5 x 3.5 x 4 mm, 36 slices, FoV: 224 mm, TR: 2000 ms, TE: 25 ms, flip angle: 90°). The number of acquisitions will be 120 (4 min) for each mental imagery and video-watching session.

**fMRI Tasks:** Subjects will perform 4 scans of hybrid mental imagery and 4 scans of video-watching of everyday task performance (e.g., preparing a meal, grocery shopping). Each fMRI scan will last 4 min. After each scan subjects will answer basic questions about the imagery and video content by pressing buttons. The total scan time will not exceed 1 hour. There will be a short post-scan debriefing to assess memory of the imagery and video content.

**fMRI Data Analysis:** The Connectivity toolbox will be used (Whitfield-Gabrieli and Nieto-Castanon, 2012). Removal of the first four scans to reach magnetization steady state, motion correction, outlier detection, coregistration of functional scans with the anatomical scan, normalization to the standard MNI template, and smoothing with an 8-mm kernel to account for inter-individual anatomical variability will be performed. De-noising steps will include the elimination of signal originating from the white matter and cerebrospinal fluid, regression of motion artifacts and outliers from the time series, scrubbing, quadratic detrending, and highpass-filtering (0.008 Hz < f < Inf). For each subject, the signal time courses during imagery and video-watching tasks will be extracted from the regions of the whole brain atlas in the Connectivity toolbox using Pearson correlation. The correlation values will be Fisher z-transformed. This analysis will yield correlation maps for imagery and video-watching tasks for second-level statistical analysis.

5. Genetic Testing    N/A

A. Describe

- i. the types of future research to be conducted using the materials, specifying if immortalization of cell lines, whole exome or genome sequencing, genome wide association studies, or animal studies are planned *Write here*
- ii. the plan for the collection of material or the conditions under which material will be received *Write here*
- iii. the types of information about the donor/individual contributors that will be entered into a database *Write here*
- iv. the methods to uphold confidentiality *Write here*

B. What are the conditions or procedures for sharing of materials and/or distributing for future research projects? *Write here*

C. Is widespread sharing of materials planned? *Write here*

D. When and under what conditions will materials be stripped of all identifiers? *Write here*

E. Can donor-subjects withdraw their materials at any time, and/or withdraw the identifiers that connect them to their materials? *Write here*

- i. How will requests to withdraw materials be handled (e.g., material no longer identified: that is, anonymized) or material destroyed)? *Write here*

F. Describe the provisions for protection of participant privacy *Write here*

G. Describe the methods for the security of storage and sharing of materials *Write here*

6. **Subject Population:** Provide a detailed description of the types of human subjects who will be recruited into this study.

There is no restriction for gender, race, or ethnicity. Fifty subjects with PD will be recruited for this study. The median age of onset of idiopathic PD is 62.4 years. In the US, the incidence of PD cases before age 40 is extremely low (Wirdefeldt et al., 2011). Therefore, individuals below the age of 40 will not be included. PD affects more males than females with a median 1.8:1 male:female ratio (Wirdefeldt et al., 2011). We will aim to reflect this ratio in subject selection. Local and non-local patients with PD are referred to our outpatient clinics. We will seek a racially and ethnically diverse enrollment. A cross-sectional epidemiological study based on Medicare records (Willis et al., 2010). 61 reported the following ratios for racial distribution of PD in the US: White:Black = 1.5 and White : Asian = 1.4. Hispanic was treated as a racial category and the White (non- Hispanic):Hispanic ratio was 1. The number of other racial categories was very small. The numbers in the planned enrollment table below were calculated based on these ratios.

